**17. Monitoring Plan to Assess Data to Ensure Safety of Subjects.**

A. Is there a monitoring plan to periodically assess the data to ensure the safety of subjects or to ensure negative outcomes do not occur?

 No  
 Yes

Explain your answer. If you answered Yes, describe the monitoring plan.

The University of Kinshasa Neurology Department and the Oregon Health and Sciences University are presently maintaining a formal research collaboration, under the direction of [name] [name]. [name] is PI of the R01 randomized RCT for the wetting method prevention of konzo, within which the proposed R21 will be embedded. They are presently sponsoring the formation of a standing data safety and monitoring board based at the University of Kinshasa Medical School as part of ongoing NIH and CDC sponsored clinical trials research program. Clinical faculty members from the bioethics program at OHSU are supporting this effort in the formation of a DSMB for the R01 study. Also, the MSU Office of Clinical Research (OCR) within the Institute for Clinical and Translational Sciences is also committed to supporting the Thrive Early psychiatry global research initiative in the formation and support of any DSMB relevant to our efforts. For the MISC caregiver training clinical trials with HIV-affected households in Uganda, that provided regulatory guidelines and lists of key membership from our program in Epidemiology, Biostatistics, and Bioethics and Humanities for the DSMB for those clinical trials. In the meantime, the R21, R01, and Sub-Contractor (INRB) PIs will be responsible for monitoring any adverse events notably breach of confidentiality related to home-based MISC training, emotional duress for caregiver evaluation of mental health and caregiving functionality, and profound neurodisability for study children that becomes evident from this domain of outcomes assessment. Monitoring will be done on a continuous basis. Any adverse events will be reported to the Institutional Review Boards (IRB) of participating institutions to ensure that appropriate action is taken. This is an appropriate strategy because the proposed intervention for the present R21 proposed study is behavioral in nature and very low risk. Likewise, the outcomes assessments specific to this R21 are on-invasive lab (urine thiocyanate

levels) or behaviorally based and established to be low-risk from prior use in our preliminary assessment work in the DRC with konzo-affected households.

**CLICK IRB:** Upload any data safety monitoring plans to the Supporting Documents SmartForm pages.

- B.** If there is a data safety monitoring committee or board, describe the composition and frequency of meetings.  Not Applicable

**18. Results and Data Sharing.**

- A.** Could this research generate any results that could be clinically relevant, including individual research results, or general, or aggregate research findings?

- No  
 Yes, clinically relevant individual research results  
 Yes, clinically relevant general or aggregate research findings

- 1.** If yes, explain what clinically relevant research results will be generated, whether they will be disclosed to subjects or others (e.g. subject's primary care physician), and if so, under what conditions. Address individual research results and/or general or aggregate research findings, as appropriate. *This also needs to be explained in the consent document.*

- B.** For other research results, select all that apply:  Not Applicable
- Overall study results will be shared directly with subjects  
 Individual results or incidental findings of individual subjects will be shared with subjects or others  
 Data will be submitted to a repository or database as part of data sharing agreement (e.g. genomic data sharing)

- 1.** Explain your selection(s), including how the data or results will be shared and with who (e.g. subject's primary care physician, data repository).

**19. Local Context and Multi-Site Study.**

- A.** Describe the locations of where the study team will obtain information or biospecimens through intervention or interaction with the subject or obtain the subjects' private identifiable information.

This study will take place in Kahemba, a district with the highest known incidence of konzo in the world. The district of Kahemba has been continuously affected by konzo since 1990. Residents of Kahemba rely heavily on cassava farming and possess very limited livestock (goat, pigs, chicken) for subsistence. During the last decade, the population of Kahemba has experienced a severe economic crisis due to the return of Congolese refugees from Angola with the end of armed conflicts in Angola. Due to food production shortfalls coupled with increased demand, residents of Kahemba have been forced to take short-cuts in the proper processing of cassava, a phenomenon that has led to an increase in food cyanogenic exposure. These short-cuts typically involve "short-soaking" the cassava (soaking the peeled tubers in water for less than the 3 days necessary for adequate fermentation), and failing to adequately dry the soaked tubers in sunlight (at least a day) before pounding the tubers into flour for storage. Coincidentally, an unprecedented rise in the number of konzo cases has been documented with prevalence up to 20% in certain villages. There is good field research clinical trial capacity so support our study in Kahemba because it is also presently the site of an NIEHS non-inferiority clinical trial. This R01 trial (2R01ES019841; PI: [name]) is evaluating the comparative efficacy of peer- versus

## HRP-503 - Template – Protocol

professional-led wetting method training (WTM) of caregivers in an effective approach for detoxifying their cassava flour before consumption. This approach is the standard of care for our present R21 study because it has been repeatedly demonstrated to reduce cyanogenic levels in poorly processed cassava flour to safe levels, even if the flour is initially very toxic due to short-cuts that have been taken in the processing of the cassava

- B.** If the study will engage employees or agents of non-MSU organizations (e.g. performance sites), explain how the employees or agents will be engaged (e.g. will they perform research procedures, will they obtain informed consent from subjects).  Not Applicable

Research staff in DRC will be managed on-site by our local partners (PRONANUT and INRB). This is highly experience staff who has participated in previous clinical trials (a parent R01 to this application). All research staff will have completed Human Subjects Research training and will be in direct supervision by Drs. [name] and [name], who will report directly to [name] (PI).

- C.** If the study involves multiple performance sites, describe the methods for communicating with engaged sites related to the protection of human subjects (e.g. any potential unanticipated problems that may involve risks to subjects or others).  Not Applicable

Drs. [name] and [name] will oversee all study activities at each site and report directly to the PI ([name]) by email or call as needed. During the enrollment period, sites will communicate with the MSU PI and co-investigators on a weekly basis through a secure conference call system to report on enrollment numbers and any issues encountered.

- D.** If there are any cultural or local contexts or requirements that may impact the protection of human subjects or present additional risks to subjects that have not otherwise been described, please describe. If research is conducted outside the state of Michigan, this could include additional state or international requirements or laws.  Not Applicable

This study will be reviewed by the local IRB in DRC (housed at PRONANUT)

- E.** If translations to a language other than English will be provided to subjects, describe the translation process.  Not Applicable

Consent and assent forms will be translated to the local language by local research staff and back translated for accuracy. Final versions will be reviewed by [name] (co-I)

***CLICK IRB: Upload translated documents to the appropriate SmartForm page(s).***

### 20. Resources and Financial Compensation and Costs.

- A.** If someone will receive a payment for recruiting the subjects, explain the amount of payment, who pays it, who receives it, and why they are being paid.  Not Applicable

The Kinshasa-based PRONANUT and INRB study teams (sub-contractor) have carried out international research studies on cassava- based health problems and thus is known and trusted in DRC. Subjects will be recruited with the full knowledge, consent and support of tribal leaders

and with the knowledgeable assent of other trusted parties, including village leaders and resident missionaries or church leaders. These parties will be informed of the study purpose, namely to assess the interplay between the body's structure and function and its exposure to natural substances in cassava. They will also be told that the initial and continued participation of the village and individual villagers is entirely voluntary. Participation includes answering a series of simple questions and providing sample of cassava flour, blood and urine at enrolment and in subsequent annual visits. Those who decide they wish to participate will be compensated equivalent of ~ \$ 10 monthly in local currency for the duration of the caregiver training interventions, either WTM or WTM/MISC).

Caregivers will be reimbursed for travel costs to the clinic visits up to \$5 USD per visit

- C. If subjects will incur additional financial costs as a result of their participation in  Not Applicable this study, explain the additional costs.

- D. Describe any resources not otherwise described elsewhere in the submission  Not Applicable (e.g. internal funding) for the protection of human subjects.

*CLICK IRB: Upload any funding materials not accessible in Kuali Coeus in the Supporting Documents SmartForm page.*

- E. If subject's biospecimens (even if identifiers are removed) may be used for commercial profit, describe whether the subject will or will not share in the commercial profit. *This also needs to be explained in the consent document.*

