## 2. Procedures.

Describe the research procedures that involve obtaining information or biospecimens about a living person through interaction or intervention and/or by obtaining their identifiable private information or identifiable biospecimens. If subjects will participate in or undergo an intervention, fully describe the intervention. If the procedures are longer than 1 page, provide a summary and include the full procedures as an attachment.

Caregiver/child dyads will be randomized (by cluster) whereby 66 of the 100 households will be selected to randomly receive MISC/WTM caregiver training to enhance caregiver mental health and functionality and early childhood development. The remaining 34 households will receive WTM only (considered the recommended standard of care for the prevention of konzo disease in at risk communities). This is in order to see if adding MISC to caregiver training enhances adherence to WTM for flour detoxification, corresponding child neurodevelopmental and caregiver functionality mental health outcomes – as compared to WTM alone for similar households. To maintain concealment of MISC training allocation, the randomization sequence was generated by the trial biostatistician located in the USA, who also serves as our clinical methodologist and biostatistician for the R01 WTM konzo prevention non-inferiority clinical trial.

The WTM intervention. The intervention will implement the WTM cassava processing technique in participating households. Twenty women with leadership and communication skills have already been trained and are implementing WTM in the R01 trial and will do the training for our WTM-only households in this R21 study. These are mothers who master the WTM technique and have been certified as trainers to train and support other small groups of other mothers. They have to be able to bring the cassava cyanogenic content to the lowest achievable level, which must be < 10 ppm as per the WHO recommendations.

The wetting method to remove cyanogens from cassava flour involves adding dry flour to a bowl and marking the level on the inside of the bowl. Water is then added with mixing, the volume of

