### 5. Reasonably Foreseeable Risks.

**A. There are (select one of the following):**

- No reasonably foreseeable risks to subjects  
 Reasonably foreseeable risks to subjects

**B. Explain the selection. *If you selected that there are reasonably foreseeable risks to subjects, describe the risks, considering physical, psychological, social, legal and economic risks.***

The major risk to enrolled subjects concerns misunderstanding of the purpose of the study, fear of the consequences of participating or not participating, stigma arising therefrom, and concern regarding study outcomes. Another potential risk is a failure to understand why a medical team is focused on prevention of konzo and cannot offer a treatment or cure for extant disease victims. Based on our prior experience in our preliminary research described in the research plan ([name] et al., 2017) as well as in the Uganda MISC clinical trial studies, we have documented no adverse effects from neurodevelopmental testing of the younger children. The same is true for the caregiver functionality and depression/anxiety (mental health) questionnaires, and HOME evaluations specific to this proposal.

**C. If you selected that there are reasonably foreseeable risks, describe the procedures for protecting against or minimizing potential risks and provide an assessment of their likely effectiveness.**

Risks relating to misunderstanding will be minimized by the process of consenting as described above, with sequential explanations provided to tribal leaders, villager groups, and individual subjects. We have protocols in place to protect human subjects from the assessments we're using and report adverse events from the R01 study which this R21 study is occurring within its jurisdiction. Data confidentiality will be ensured by the procedures explained above, including the use of unique numbers to identify enrollees, and the secure storage of identifying personal biodata (including a photograph) on the front page of the questionnaire that has been separated from other data fields on the questionnaire. These procedures are expected to be effective since the INRB sub-contractor is experienced in the conduct of human research studies to international standards. Any subject with a condition that requires medical attention will be referred to the general hospital serving the area of interest.

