**1. Please explain your selection(s).**

Participation also requires receiving information on how to process cassava so that it is safe to eat. If and when the village tribal leader grants permission, groups of villagers will be invited to assemble and learn why the team has visited their village. The Kinshasa study team will repeat to the villagers the information previously provided to the tribal leaders. They will be encouraged to ask questions to which answers will be provided. Konzo will be familiar to the villagers, but they may not understand the causal connection between the consumption of cassava and the induction of walking difficulty. In particular, since cassava is a staple that provides a major source of nourishment that keeps them alive, there may be disbelief that a causal connection with disease could be possible. Other explanations for walking difficulties may be offered by the villagers, including punishment for undefined wrongdoing, a curse placed upon villagers by another tribal group, or the result of a natural event such as a flood or

a drought. Explanation that studies have shown that other people both near and far also develop “tied legs” if they do not wash their cassava roots for a sufficient period of time usually overcome doubts and focus attention on the principal cause of konzo. Great care must be taken to explain that cassava is an important and healthy food for the community provided it is properly prepared for human consumption. Since women of the village have major responsibility for food preparation and take pride in providing adequate nutrition for their family members, optimal food preparation is a subject of considerable interest and pride. Villagers will be familiar with the fact that children and women of childbearing age are the most heavily affected by konzo (relative to adult men), and it will therefore be logical that women and children are subjects of special importance to the study team.

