**13. Consent Process.**

**A.** If the study involves adults, consent will be obtained from (select appropriate option(s)):  Not Applicable

- All subjects
- Some subjects
- No subjects (consent will not be obtained)

*CLICK IRB: Upload the consent document, script, etc. (including translations) to the Consent Forms and Recruitment Materials SmartForm page, Question 1.*

**B.** If the study involves children, parental permission will be obtained from (select appropriate option(s)):  Not Applicable

- Both parents or guardians (unless one parent is deceased, unknown, incompetent, or not reasonably available, or when only one parent has legal responsibility for the care and custody of the child)
- One parent or guardian
- Will not be obtained

*CLICK IRB: Upload the parental permission forms to the Consent Forms and Recruitment Materials SmartForm page, Question 1.*

**C.** If the study involves children, child assent will be obtained from (select appropriate option):  Not Applicable

- All children
- Some children
- Will not be obtained

*CLICK IRB: Upload the child assent form to the Consent Forms and Recruitment Materials SmartForm page, Question 1.*

**D.** Describe the consent process, including an explanation of your selection(s) above. If the study involves screening activities, please describe whether consent will be obtained and if consent will not be obtained, explain how the screening data will be used. If only some subjects will provide consent, explain who will or will not provide consent. If only some children will provide assent, explain which children will and will not provide assent.

Consenting will be performed by a member of the Kinshasa team on an individual basis after subjects have participated in the group meeting. Each subject will be asked to explain the purpose of the study: correct answers will be reinforced, and incorrect answers will be corrected with further information until the subject has a clear understanding. The subject will be informed they are free to accept or decline the invitation to participate and, if they choose to accept, they may withdraw at any time without recourse or penalty. Before making a decision whether to accept or decline, they will learn that participation in the study means the following: the study will have

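### The study purpose given to leaders, and repeated to villagers, leaves out the randomised comparison of MISC/WTM with WTM only

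*Combined protocol and SAP*

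**What the plan says.** The combined protocol describes community entry in two places. Section 20 (Resources and Financial Compensation and Costs) covers recruitment through tribal leaders and other trusted parties. These people are to be "informed of the study purpose, namely to assess the interplay between the body's structure and function and its exposure to natural substances in cassava", and told that the participation of villages and individuals is voluntary. The next sentence describes participation as "answering a series of simple questions and providing sample of cassava flour, blood and urine at enrolment and in subsequent annual visits". The one after it sets a monthly payment "for the duration of the caregiver training interventions, either WTM or WTM/MISC".

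Section 12.D.1 makes the leader's agreement the way into the village: "If and when the village tribal leader grants permission, groups of villagers will be invited to assemble". It continues: "The Kinshasa study team will repeat to the villagers the information previously provided to the tribal leaders".

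Section 5.B states: "The major risk to enrolled subjects concerns misunderstanding of the purpose of the study". Section 5.C answers that risk with explanations given in turn to tribal leaders, groups of villagers and individual subjects.

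Section 2 (Procedures) gives the reason for randomising: "This is in order to see if adding MISC to caregiver training enhances adherence to WTM for flour detoxification", together with child neurodevelopment and caregiver functioning and mental health, compared with WTM alone. Section 13.D adds a comprehension check at individual consent: "Each subject will be asked to explain the purpose of the study: correct answers will be reinforced".

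**The concern.** The purpose to be given to leaders reads as that of an observational study of exposure and bodily function. It does not say that the study tests a caregiver training programme, that two forms of training are compared, or that chance decides who receives which. Those are the facts a community leader would need in order to give informed permission for this trial.

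The plan's own safeguard is what makes this matter. Misunderstanding of the purpose is ranked as the main risk to subjects, and the remedy is a chain of three explanations. If the first two links omit the intervention and the comparison, the remedy helps to produce the misunderstanding it is meant to prevent. At stake are the quality of community permission and the consistency of what mothers hear before individual consent.

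**Working it through.** The plan states no figure on this point and no arithmetic applies. The check sets the sections side by side.

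**1. Stated purpose against the aims.** Section 1 lists three aims:
- feasibility of the year-long MISC/WTM programme;
- whether MISC improves WTM adherence, and with it flour cyanogens, urinary thiocyanate, and child and caregiver outcomes;
- whether the gains are mediated by caregiver wellbeing and functioning.

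The purpose in Section 20 is none of these. Exposure and function do appear among the Aim 2 outcomes, so the sentence is related to the trial, but it leaves out the intervention and the comparison.

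**2. Participation sentence against the procedures.**

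| Item | Section 20 participation sentence | Elsewhere in the protocol |
|---|---|---|
| Timing | enrolment, then annual visits | baseline, 6 months and 12 months (Section 2) |
| Training | not mentioned (the payment sentence that follows names both programmes) | 12 months of biweekly home sessions in both arms (Section 3.A) |
| Child testing | not mentioned | neuropsychological battery at each assessment (Section 2) |
| Filming | not mentioned | 15 minutes of caregiver and child interaction; consent to it is a condition of eligibility (Section 2) |
| Random assignment | not mentioned | Sections 2, 12.A and 12.B |

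The timing row is a direct inconsistency. The other rows are omissions from a sentence that does not claim to be complete.

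**3. How far the wording travels.** Step one of the Section 5.C chain is the leaders, who receive the Section 20 purpose. Step two is the village group, which under Section 12.D.1 receives the same information. Step three is individual consent. So the incomplete purpose is carried at two of three steps.

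**4. What step three repairs.** Section 13.D provides one-to-one consent and a teach-back that continues until the subject understands. It discloses the caregiver and child outcomes and says that a mother may be chosen for the MISC arm. It also provides a separate consent for filmed training sessions. That is substantial. Three gaps remain:
- The section does not write out the purpose that counts as a correct answer.
- It speaks of intervention studies against konzo as something in the future. That may mean a larger successor trial, but it does not make clear that the present study is itself an intervention trial.
- It comes after the leader's permission and the village meeting, so it cannot correct what was said there.

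**The case against.** The strongest reply is that Section 20 is a short narrative under a form question about recruitment payments, not a script. Only the purpose and the voluntary nature of participation are attributed to what leaders hear. The participation sentence is not exhaustive and is not said to be read to them, and the payment sentence that follows names both training programmes. Section 12.D.1 adds that participants receive information on processing cassava safely. Mothers learn of the MISC arm before they decide. All of this stands. It limits the point to the purpose sentence, its repetition to villagers and the visit timing. It does not remove the point, because the purpose sentence is explicit about what leaders will be told.

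A reader might infer three stronger things that the documents do not support.

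- *That permission is sought for a different study.* Exposure and neurodevelopment are Aim 2 outcomes, and Sections 9.A and 11 expect knowledge of neurotoxicity and biomarkers as a product. The stated purpose is incomplete rather than unrelated.
- *That surprised villages would withdraw unevenly between arms.* Section 3.A gives the WTM-only arm biweekly home sessions too, and Section 2 makes filmed interactions a condition of enrolment for all. What differs is the MISC content and the recorded quality-assurance sessions. Nothing in the protocol reports village refusal.
- *That the loss can be sized from households per village.* The number of villages is not given, and the cost of losing one is the same whatever leaders are told. Such a figure would not measure this defect.

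Nor can it be shown that the teach-back has two competing right answers. Section 13.D adopts no wording, and the consent forms are not in the copy reviewed.

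**Conclusion.** The point holds in a limited form. A stated procedure is wrong as written: leaders, and through them villagers, are given a purpose that omits the randomised training comparison, at two of the three steps on which the plan relies against the risk it ranks first. The participation sentence also gives a visit schedule that conflicts with Section 2. Individual consent partly corrects the purpose for enrolled mothers, but not for leaders and village groups when permission is given.

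The effect is on participant protection. There is no change to the estimand, sample size, allocation or analysis, and no numerical size is claimed. The conclusion assumes that field staff follow Section 20 as written. If a fuller community script or consent form exists, the repair is simply to bring Section 20 into line with it. The change is worth making before community entry, but it does not call the design into question.

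**What to change.** 1. Replace the purpose and participation sentences in Section 20 with text drawn from Sections 1, 2 and 3.A: the study tests whether adding MISC to WTM improves flour detoxification, child development and caregiver wellbeing; there are two training arms assigned at random; home sessions run biweekly for a year; children are tested; mothers and children are filmed; and assessments are at baseline, 6 and 12 months.
2. Use the same text at the village meeting in Section 12.D.1, and name it in Section 13.D as the reference answer for the teach-back.
3. In Section 13.D, reconcile the reference to future intervention studies with the fact that this study is an intervention trial.
4. Settle how randomisation is described before finalising the script. Section 12.A speaks both of randomisation at village level and of selecting 66 of the 100 households after baseline. Section 12.B randomises villages to MISC/WTM or WTM only, but also says that villages are assigned to peer-led or specialist-led training. Leaders should be told the unit of assignment once these statements agree.

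The cost is redrafting, translation of the revised text where it is used in the field, and an IRB amendment. No visits, staff or measurements are added. Item 4 makes this slightly more than a wording change, because the protocol must first be consistent about what is randomised.
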